7.7.2.2 Pulmonary Vein Isolation

Ablation of the PVs will be performed according to the IFU documents and institutional practice.

Ablation will be attempted in every clinically relevant PV, including any vein with an electrically active muscular sleeve. Small anomalous PVs that are electrically silent need not be attempted.

The use of ICE is recommended but not required for Pulsed Field Ablation procedures.

All catheter exchanges should be carefully performed to avoid introducing air bubbles into the FARADRIVE Steerable Sheath.

Esophageal temperature monitoring, esophageal cooling and esophageal deviation are unnecessary during PVI and PWI ablation with the FARAWAVE PFA Catheter and should not be utilized.

7.7.2.3 Posterior Wall Isolation

Following PVI ablation, LAPW ablation will be performed according to the IFU documents and institutional practice.

LAPW ablation will be performed in the area below the superior aspect of the superior PVs, above the inferior aspect of the inferior veins, and between the insertions of the left sided and right sided PVs. In the event the PW is found to be electrically isolated following PVI, LAPW ablation will still be performed using the same anatomically guided approach until there is sufficient overlap between PFA application sites. No ablation in other locations, including the left atrial appendage, is permitted.

LAPW ablation should be guided by electroanatomical mapping, ICE and / or fluoroscopy to ensure the entire area of LAPW is ablated with the appropriate amount of overlap between PFA application sites.

All catheter exchanges should be carefully performed to avoid introducing air bubbles into the FARADRIVE Steerable Sheath.

Esophageal temperature monitoring, esophageal cooling and esophageal deviation are unnecessary during PVI and LAPW ablation with the FARAWAVE PFA Catheter and should not be utilized.

7.7.2.4 Assessment of Isolation and Phrenic Nerve Function

Assessment of Isolation

After the completion of the planned PV and LAPW ablations, isolation will be assessed as:

- The isolation of all attempted PVs at least 20 minutes following the last PFA application in each respective vein by entrance block performed with or without adenosine testing, AND
- The isolation of the LAPW at the end of the LAPW ablation, performed with or without adenosine testing, via interrogation by multipolar diagnostic catheter or 3D electroanatomical

mapping. If electroanatomical mapping is used, electrograms demonstrating PWI are required per **Section 7.18**. At the Investigator's discretion, exit block pacing of the PW may be performed to detect any epicardial exit pathways.

Additional PV and LAPW ablation as described above may be performed as needed at any time to achieve complete PVI and PWI. Alternative dosing or fewer applications may be performed as needed for subject welfare, technical difficulties, or anatomical challenges and will not constitute a Treatment Failure if electrical isolation is still confirmed as required. In the event that touch-ups are performed after the initial isolation assessment, further waiting periods are not required.

Assessment of Phrenic Nerve Function

Once all PV and LAPW ablation is completed and isolation is confirmed, the functional status of both phrenic nerves will be assessed per Investigator standard of care (e.g., radiographically either by pacing, fluoroscopy, or a sniff test.⁷)

7.7.2.5 CTI Ablation

The following subjects will undergo CTI ablation with the FARAPoint PFA Catheter:

- Required: For subjects with a history of CTI-mediated (typical) AFL and
 - Who have not had a CTI ablation procedure, or
 - Who have had a CTI ablation procedure but have recurrent CTI conduction.
- Required: Subjects who manifest CTI-mediated AFL (spontaneous or induced) during the Index Procedure
- At Investigator discretion: Subject welfare indicates that CTI ablation should be performed.

CTI Ablation with the FARAPoint PFA Catheter will be performed according to the IFU documents and institutional practice. Per the FARAPoint Catheter IFU, no more than two energy applications should be delivered at any given catheter placement. Repeat placement of the FARAPoint Catheter at nearly identical locations should be avoided unless there is a clear clinical need for such placements.

The FARAWAVE Catheter is not allowed to complete any CTI lesion.

CTI ablation with the FARAPoint PFA Catheter must adhere to the following protocol requirements in order to mitigate the risk of coronary spasm during ablation application.

No ablations outside CTI with the FARAPoint PFA Catheter are allowed.

The following prophylactic workflow is required to be followed when CTI ablation is performed with the FARAPoint PFA Catheter:

- **Pre-Treatment (Required)**: Administer a three milligrams (3mg) nitroglycerin IV bolus via the FARADRIVE sheath (or other sheath with central access) approximately one minute prior to the first PFA application at the anterior position of the CTI line.
- **During Ablation (Required)**:

⁷ If anesthesia necessitates, a pre-discharge fluoroscopic sniff test or inspiration / expiration CXR may be acceptable. See **Section 7.8**.

- Depending upon procedure duration and patient condition, administer an additional 2mg IV bolus via the FARADRIVE sheath (or other sheath with central access) approximately two (2) minutes apart until the ablation is complete or a maximum total of 9mg IV of nitroglycerin has been administered.
- If bidirectional block (BDB) is assessed and not present and additional ablation lesions are required in the anterior aspect of the cavo-tricuspid isthmus line, Investigator discretion will determine whether to administer an additional 2-3 mg of nitroglycerin IV via the FARADRIVE sheath (or other sheath with central access) prior to re-ablation.

Adjustments to the nitroglycerin dosing protocol defined above are allowed per Investigator discretion based on patient condition, but the rationale for any changes to the defined workflow will be collected. Failure to administer any pre-treatment nitroglycerin will be a protocol deviation.

Vasopressors may be administered per physician discretion given that comorbidities, drug regimens, mode of anesthesia, and baseline blood pressure will vary among subjects.

200 micrograms (μ g) of phenylephrine should be administered prior to the first dose of nitroglycerin. If not administered, the rationale will be collected.

Additional vasopressor doses may be administered at the discretion of the physician depending upon the blood pressure response to nitroglycerin. Investigators may choose to administer a different vasopressor depending upon the clinical profile of the subject. All medications administered during the procedure, dose, route and timing of administration in relation to the PFA applications will be recorded.

For those subjects with a known left dominant coronary artery system, as defined by a left heart catheterization or coronary CT angiography, the above prophylactic nitroglycerin workflow is not required. The proximity of the catheter to the artery may be directly visualized in real-time via intracardiac echocardiography. Routine hemodynamic monitoring for patients undergoing sedation and cardiac ablation is recommended.

A post-procedure 12-lead ECG will be recorded following CTI ablation to assess absence of ischemia. If the post-procedure ECG shows any ischemic changes, a transthoracic echocardiographic assessment is **required** the same day as the procedure to assess if intraventricular wall motion abnormalities are observed compared to the pre-procedure echocardiographic assessment (Section 7.8).

After CTI ablation is completed, BDB will be assessed, and if necessary, additional applications may be performed until BDB is confirmed. The CTI ablation data will be documented in the CRF.

7.7.2.6 Other Ablations for Atrial-Dependent Arrhythmias

When the Investigator determines that subject welfare requires intervention for either an accessory pathway, AVNRT or spontaneously occurring treatment-emergent AFL or AT, ablation for these arrhythmias may be performed using any commercially available RF ablation catheter. These ablations must not be performed with the FARAPULSE PFA System and should be performed after all ablation with the FARAPULSE PFA System is complete. These permitted ablations and the associated data will be documented in the CRF and do not constitute Persistent AF Acute Procedural Failure. FARAWAVE usage is not allowed to complete any lesion outside of the PVs and LAPW, as described in the IFU.

Ablation for an arrhythmia that is provoked only by catheter manipulation or is only inducible by pacing or pharmacologic stimulation is not permitted.

IMPORTANT: FARAWAVE cannot be used to complete any lesion in the Left Atrium except for the PVs and LAPW, under any circumstances.

FARAWAVE cannot be used in any other location, including the right atrium or either ventricle!

7.7.3 Rescheduled Index Procedure

If, at the Index Procedure, the subject is found to have inadequate pre-procedural anticoagulation, a current atrial thrombus, COVID-19, or other temporarily disqualifying condition, the subject may have their Index Procedure rescheduled not later than 45 days later. The Rescheduled Index Procedure will otherwise follow the data and procedural requirements of **Section 7.7.2**.

The Rescheduled Index Procedure must be scheduled within 45 days of the Index Procedure, and only one Rescheduled Index Procedure may be allowed; otherwise, the subject will be exited from the study as an Intent Subject.

This rescheduling is permissible and does not create an Acute Procedural Failure. The subject remains a potential Treatment Subject.

References to “Index Procedure” in this protocol should be assumed when appropriate to include “Rescheduled Index Procedure” as well if not otherwise specified.

7.8 Pre-Discharge Assessment

Subjects should be prescribed a form of systemic anticoagulation treatment for at least two months following the ablation procedure. See **Section 7.3** regarding post-ablation anticoagulation requirements.

Type of Assessment: In-person at investigational site

Prior to hospital discharge, study data will be collected including but not limited to:

- Adverse events
- Hematocrit, hemoglobin, electrolytes, BUN, creatinine
- 12-lead ECG to document the subject's rhythm and if any new conduction disturbances are observed.
 - A 12-lead ECG collected at the end of the Index Procedure / Rescheduled Index Procedure after all ablation was complete also fulfills this data collection requirement.
- If the post-ablation ECG collected at the end of the Index Procedure/ Rescheduled Index Procedure showed any new ischemic changes the following are required:
 - An additional 12-lead ECG at Pre-Discharge
 - A transthoracic echocardiographic assessment (TTE)
 - The TTE is required the same day as the procedure to assess if ventricular wall motion abnormalities are observed compared to the pre-procedure echocardiographic assessment.
- Data regarding the use, changes in or discontinuation of anticoagulation, rate control and / or AADs.
- Occurrence, date, indication and outcome of any post-procedure cardioversion(s)
- Phrenic nerve assessment, as only applicable:

[figure not shown]
- If the function of both phrenic nerves could not be confirmed at the end of the Index Procedure / Rescheduled Index Procedure, a radiologic examination of the diaphragm (fluoroscopic sniff test or inspiration / expiration CXR)
- If the post-Index Procedure / Rescheduled Index Procedure fluoroscopy indicated diminished phrenic nerve response and resolution has not been previously demonstrated, complete a radiologic examination of the diaphragm

Pre-Discharge Stroke Evaluation:

- NIHSS score by NIHSS-certified site personnel after the effects of anesthesia have fully resolved.
- If either of the following occurs:
 - The post-procedure NIHSS score has increased by 1 or more points over the pre-procedure NIHSS score OR
 - There is a clinical suspicion of stroke or TIA

Then a consulting neurologist will perform a stroke assessment and include the results of a concurrent brain DW-MRI scan. This assessment will be sufficient to determine with reasonable certainty whether a stroke, TIA or neither have occurred, using the definitions in **Table 3.3-2**. Please refer to **Figure 7-1**.

Figure 7-1: Pre-Discharge Stroke Evaluation

7.9 Day 7 Safety Assessment

Type of Assessment: Remote
Window: Days 7 – 11
The Day 7 Assessment is essential to establish the primary safety endpoint and every effort must be made to complete this assessment between Day 7 and Day 11.
If the assessment is delayed, the onset date of an AE must be elicited as carefully as possible to establish whether it occurred within the interval between the ablation procedure and Day 7, or thereafter.

Subjects will be assessed remotely between Day 7 and 11 post-Index Procedure / Rescheduled Index Procedure. Any subject who continues to be hospitalized at the time of the assessment will have their Day 7 assessment performed in-hospital.

Study data will be collected by interview, including but not limited to:

- Adverse events
- Data regarding the use, changes in or discontinuation of anticoagulation, rate control and / or AADs.

- Recurrent arrhythmia, cardioversions, ablations, or hospital admissions since discharge
- Site staff will confirm successful LUX-Dx insertion and LATITUDE Clarity transmissions (if available)
- The date and communication method(s) used to collect the data remotely.

7.10 Day 30 Safety Assessment

Type of Assessment: Remote; In-person allowed
Window: Days 30 – Day 37
The Day 30 Assessment is essential to establish the primary safety endpoint and every effort must be made to complete this assessment between Day 30 and Day 37.
If the assessment is delayed, the onset date of an AE must be elicited as carefully as possible to establish whether it occurred within the interval between the ablation procedure and Day 30, or thereafter.

AAD Treatment: Between the Day 30 Assessment and the Day 90 Assessment – the subject should be assessed for AAD continuation. See Section 7.11.

Discharged subjects will be assessed remotely between Day 30 and Day 37 post-Index Procedure / Rescheduled Index Procedure. Any subject who is hospitalized at the time of the assessment will have their Day 30 assessment performed in-hospital.

Study data will be collected by interview including but not limited to:

- Adverse events
- Data regarding the use, changes in or discontinuation of anticoagulation, rate control and / or AADs
- Recurrent arrhythmia, cardioversions, ablations, or hospital admissions since 7-day telephonic assessment
- Site staff will confirm ICM programming and successful LATITUDE Clarity transmissions since last assessment
 - Assess for any recurrence of AF/AFL/AT
 - Any reported AFL recurrence will require a 12-lead ECG for ACL adjudication
 - Confirm ICM programming parameters
 - Any programming outside of the defined nominal parameters (Section 7.6) prior to a confirmed recurrence of Detectable AF, AT or AFL must be entered into the EDC and justification provided.
 - ICM may be reprogrammed, as needed, to facilitate appropriate arrhythmia identification and investigator notification after the subject experiences a confirmed recurrence of Detectable AF, AT or AFL.
- The date and communication method(s) used to collect the data remotely
- If the post-Index Procedure / Rescheduled Index Procedure fluoroscopy indicated diminished phrenic nerve response and resolution has not been previously demonstrated, the patient must return for a radiologic examination of the diaphragm between Day 30 and Day 37.

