1.4 Summary

The present IDE study incorporates the treatment strategy for PersAF ablation utilized in the PersAFOne studies using the FARAWAVE PFA Catheter for electrical isolation of the PV and isolation of the LAPW region between the PVs, coupled with selective CTI isolation using the FARAPPOINT PFA Catheter. In addition to further characterizing PVI, PWI, and CTI ablation, this study will also give the opportunity to explore the effectiveness of ablation therapy assessed through a continuous source of recording (ICM) and evaluate recurrence rates and AF burden which may help to define a standard in the PersAF population useful for the design of future studies.

2 Device Description

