Treatment Success as defined in **Section 3.4** but counting subjects with any re-ablation for AF, AFL, or AT as Treatment Failures

- **Off Drug Treatment Success**

Treatment Success as defined in **Section 3.4** but counting subjects treated with any Class I / III AAD after Day 90 as Treatment Failures

- **Re-Ablation Rate**

Defined as the proportion of subjects who receive one or more re-ablations during study follow-up for AF, AFL, or AT, at any time during follow-up, and subdivided by re-ablation during Days 0 – 90 and by Days 91 and thereafter. CTI only re-ablation is excluded for subjects who did not receive CTI ablation with the FARAPPOINT catheter.

- **AF, AFL, and AT Burden**

Descriptive statistics on AF, AFL, and AT burden, as defined in Section 23.2 and assessed during the observation period from Day 91 to Day 360 Assessment. AF, AFL, and AT burden will also be calculated for the days from LUX-Dx activation to the Index/ Rescheduled Index Procedure (up to 30 days pre-procedure) and compared to the burden calculated from Day 91 to Day 360 Assessment. Additionally, AF, AFL, and AT burden statistics from Day 91 to Day 360

will be stratified by recurrence based on LUX-Dx detected AF, AFL, or AT using various episode duration thresholds.

- **Healthcare Utilization by AF, AFL, and AT Burden**

Healthcare utilization, defined by outcomes of all-cause hospitalization, cardioversion for AF, AFL, or AT recurrence outside of an ablation procedure, re-ablation for AF, AFL, or AT and unscheduled cardiovascular follow-up assessments, will be compared between subjects grouped by AF, AFL, and AT burden from Day 91 to Day 360 Assessment. Burden groups will include rates of 0%, 0-0.1%, 0.1-1%, 1-5%, 5-10%, and >10% AF, AFL, and AT burden.

- **Healthcare Utilization by AF, AFL, or AT Recurrence Duration**

Healthcare utilization, defined by outcomes of all-cause hospitalization, cardioversion for AF, AFL, or AT recurrence outside of an ablation procedure, re-ablation for AF, AFL, or AT and unscheduled cardiovascular follow-up assessments will be compared between subjects grouped by longest duration of AF, AFL, or AT captured by LUX-Dx (based on continuous monitoring) between Day 91 and Day 360 Assessment. Groups will include no recurrence and longest duration of 0-6 minutes, 6 minutes – 1 hour, 1-6 hours, 6-24 hours, and \geq 24 hours.

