Tachy Response	Less	Yellow Alert
AT Detection	On	Alert for Tachy Events –
AT Duration	4 hours at 110 bpm	On Red Alert

Any programming outside of these nominal parameters prior to a confirmed recurrence of Detectable AF, AT or AFL must be entered into the EDC and justification provided.

7.7 *Index Procedure / Rescheduled Index Procedure*

7.7.1 *Index Procedure / Rescheduled Index Procedure Data Collection*

Type of Assessment: In-person at investigational site
The performance of the Index Procedure / Rescheduled Index Procedure and the Pre-Discharge Assessment both require an in-person assessment. The Index Procedure / Rescheduled Index Procedure must be deferred if this is not possible.

Procedural data will be collected including but not limited to:

- The results of transesophageal echocardiography (TEE) or volumetric CT within 48 hours prior to procedure, or intracardiac echocardiography (ICE) prior to transseptal puncture, utilized for exclusion of LA thrombus.
- Pregnancy test (all women of childbearing potential if the baseline pregnancy test was obtained more than 30 days prior to the Index Procedure / Rescheduled Index Procedure)
- Documentation of PVI for each attempted vein, of PWI, and if performed, of CTI BDB
- Post-ablation electroanatomical maps, if performed with Rhythmia
- The functional status of both phrenic nerves will be assessed radiographically pre and post ablation.
- Method of sedation or anesthesia
- Whether adenosine was used to confirm PVI and / or PWI
- Whether a post-procedure cardioversion was performed
- Adverse events
- For the 3D mapping system: Manufacturer and model, when applicable
- 12-lead ECGs pre- and post-ablation
- Procedural times
- Ablation data

- Procedural anticoagulation data:
 - For subjects on a DOAC whether DOAC therapy was interrupted for procedure
 - For subjects on warfarin, a pre-ablation international normalized ratio (INR) value
 - Procedural heparin administration and timing
- Device deficiencies and malfunctions

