7.11 Day 90 Assessment

Type of Assessment: In-person at investigational site required; remote only for documented COVID-19 related disruption.
Window: 90 ± 14 Days
If a COVID-19-related disruption prevents an in-person assessment within window: 
As much data as possible may be collected remotely.The absence of a 12-lead ECG during a remote assessment is not a protocol deviation.If a radiologic examination is required due to prior diminished phrenic nerve response, an inspiration / expiration chest X-ray (CXR) performed in-person or at another healthcare site may be substituted.
AAD Treatment: During the Blanking Period the subject should be assessed for AAD continuation. At Investigator discretion, Class I / III AADs may be stopped to allow assessment of the subject's potential for off-drug freedom from recurrent AF, AFL, or AT. Subjects who require continued AAD treatment may be continued; preferably with a Failed AAD . Using a Non-Failed AAD or amiodarone would create an unnecessary Treatment Failure.

Subjects will be assessed at Day 90 ± 14 days following the Index Procedure / Rescheduled Index Procedure. Study data will be collected at the Day 90 Assessment including but not limited to:

- Adverse events
- Data regarding the use, changes in or discontinuation of anticoagulation, rate control and / or AADs
- Recurrent arrhythmia, cardioversions, ablations, or hospital admissions since last assessment
- Site staff will confirm ICM programming and successful LATITUDE Clarity transmissions since last assessment
 - Assess for any recurrence of AF/AFL/AT
 - Any reported AFL recurrence will require a 12-lead ECG for ACL adjudication
 - Confirm ICM programming parameters
 - Any programming outside of the defined nominal parameters (Section 7.6) prior to a confirmed recurrence of Detectable AF, AT or AFL must be entered into the EDC and justification provided.
 - ICM may be reprogrammed, as needed, to facilitate appropriate arrhythmia identification and investigator notification after the subject experiences a confirmed recurrence of Detectable AF, AT or AFL.
- Cardiac rhythm as determined by a 12-lead ECG at the time of the assessment (in-person assessment only). All 12-lead ECGs for Treatment Subjects will be provided to the Arrhythmia Core Laboratory (ACL).

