7.14 Re-Ablation Procedures

7.14.1 Re-Ablation Procedure within the Blanking Period

For subjects undergoing a first re-ablation procedure within the Blanking Period for Detectable AF, AFL or AT, the procedure will be performed by the investigator under the procedures and data

requirements of **Section 7.7.1**, modified to assess and treat only those locations required, and including the pre- and post-procedure NIHSS.

The FARAPoint PFA Catheter will not be utilized for any re-ablation procedure. If repeat ablation is required for CTI-mediated flutter, any commercially available BSC RF catheter will be used. Such re-ablation using the methods and devices described in **Section 7.7.1** does not constitute a Treatment Failure.

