Blanking Period	
An interval in which recurrent AF, AFL or AT, cardioversion or a first re-ablation do not constitute Treatment Failure beginning on Day 0 and running for 90 days thereafter.
 
 • The Blanking Period has no impact on the assessment of AEs. • For subjects with only an Index Procedure, the Blanking Period will be Day 0 to Day 90 inclusive. • For subjects who require a Rescheduled Index Procedure, the Blanking Period will be the Study Day of the Rescheduled Index Procedure (Day 0) plus 90 days inclusive • For subjects treated with a Non-Failed AAD during the Blanking Period, a Treatment Failure due to the use of that drug only occurs if there is continued use of that drug following the earlier of either the Day 90 visit or Day 104.
(Persistent AF) Chronic Success	Defined in Section 3.4.2.
Composite Serious Adverse Events	Composite Serious Adverse Events are defined in Section 3.3.
COVID-19 Related Disruptions	A disruption to any study procedure resulting directly or indirectly from the COVID 19 pandemic, including but not limited to subject illness, study site restrictions and limitations, shipping / manufacturing interruptions, significant changes in regulatory guidance and / or governmental restrictions on travel, association, and the prioritization of healthcare resources.
Dates	
 • Consent Date: The date a subject signs the ICF. • Exit Date: The date on which a subject's study participation ends. • Onset Date: The date on which a condition or AE begins. • Start Date: Day 0, the date of the Index Procedure or Rescheduled Index Procedure
Day (or Study Day)	A Day is an enumerated day of follow-up that begins on an Enrolled Subject's Start Date (Day 0).

Term	Definition

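### Phase 2 lets the LUX-Dx be reprogrammed after a recurrence inside the Blanking Period, so a subject still at risk for the primary effectiveness endpoint can enter the Day 91–360 evaluation on non-nominal detection settings

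*Combined protocol and SAP*

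**What the plan says.** Appendix A 7.6 fixes the initial detection settings in Table 7.6-1, among them an AF duration of 4 minutes and an AT duration of 4 hours at 110 bpm. It then gives the recording rule: "Any programming outside of these nominal parameters prior to a confirmed recurrence of Detectable AF, AT or AFL must be entered into the EDC", with a justification.

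The Day 30 section (7.10, window Days 30–37) tells sites to "Confirm ICM programming parameters". It repeats the recording rule and adds the permission: "ICM may be reprogrammed, as needed, to facilitate appropriate arrhythmia identification and investigator notification after the subject experiences a confirmed recurrence of Detectable AF", continuing to AT and AFL. The same permission stands in 7.11 (Day 90), 7.12 (Day 180), 7.13 (Day 360) and 7.15 (unscheduled visits).

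The Blanking Period (23.2) is "An interval in which recurrent AF, AFL or AT, cardioversion or a first re-ablation do not constitute Treatment Failure beginning on Day 0" and lasts 90 days. Section 7.14.1 uses the endpoint term for events in that interval: "For subjects undergoing a first re-ablation procedure within the Blanking Period for Detectable AF, AFL or AT".

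For the PEE, 8.1.2.3 and the definition of Detectable AF, AFL or AT in 23.2 count stored LUX-Dx AF or AT episodes that overlap simulated post-blanking monitoring windows. Symptomatic recordings and 12-lead ECGs also count. Burden (3.5.2) is "assessed during the observation period from Day 91 to Day 360 Assessment", and the longest-episode groups use the same period. One stated purpose of Phase 2 (1.4) is to "evaluate recurrence rates and AF burden which may help to define a standard in the PersAF population".

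**The concern.** The device settings are part of the outcome measurement. Section 2.3.1 says that the monitor records when it detects an arrhythmia under its programmed settings, so a change of AF or AT settings changes which episodes are stored.

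The trigger for allowing a change is itself prognostic, because subjects with early recurrence are plausibly those more likely to recur later. If some of them start Day 91 on different settings, measurement is no longer uniform across the cohort and the difference is tied to expected outcome.

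Two things are at stake. One is the comparison of the PEE with the 40% performance goal. The other is the set of burden and longest-episode summaries from which Phase 2 hopes to derive a standard. Section 8.1.2 itself names variable ICM programming among the methodological inconsistencies of earlier ICM studies.

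**Working it through.** **Step 1: does the permission operate inside blanking?** Days 30–37 lie wholly within Days 0–90, and the permission is printed for that visit. Sections 7.12, 7.13 and 7.15 contain, close to the permission, an instruction to upload documentation of a recurrence. That instruction is limited to the first recurrence after blanking; the permission is not.

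**Step 2: which blanking recurrences can meet the definition?** Definition 23.2 has three LUX-Dx routes plus the 12-lead ECG.
- Overlap with a simulated event-monitor window: not available, because only post-blanking windows are analysed (8.1.2.3).
- Overlap with a simulated Holter: not available, because these fall the day before the Day 180 and Day 360 visits.
- Adjudicated patient-initiated recording with at least 30 seconds of arrhythmia: available.
- Arrhythmia throughout a 12-lead ECG with at least 10 seconds of interpretable signal: available.

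In practice the affected group is those with a symptomatic recording or a positive ECG in blanking. Appendix A does not define what makes a recurrence confirmed.

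**Step 3: what follows for that subject?** The recurrence is not a failure, so PEE follow-up continues. No section requires Table 7.6-1 values to be restored by Day 91. Settings are checked at visits, but the rule on EDC entry and justification ends at the recurrence.

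**Step 4: is it covered in the analysis?** Section 8.3.3.6 addresses the 4-hour AT setting and 8.3.3.7 addresses S-ECG storage. Sections 8.3.4 and 8.3.7 include the LUX-Dx model. None addresses changed settings.

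**Step 5: the plan's own figure.** Inputs from 8.1.2.2: expected rate 55%, goal 40%, one-sided 0.025, exact binomial, 10% attrition. With n = 122, the smallest r with P(X ≥ r | 0.40) ≤ 0.025 is r = 60. This gives exact alpha 0.0248 and power P(X ≥ 60 | 0.55) = 0.916, against a stated 90%. With attrition, 122 / 0.9 = 135.6, rounded up to 136. The figure reproduces.

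**Step 6: how sensitive is the test? (illustration only)** Let e be the net share of all subjects whose failure is missed because their settings differ. The documents give no value for e; 0 to 5 points is an assumed range. P(pass) = P(X ≥ r | n, 0.40 + e) when true success is 40%:

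| e (points) | n = 122, r = 60 | n = 232, r = 109 |
|---|---|---|
| 0 | 0.025 | 0.018 |
| 1 | 0.041 | 0.038 |
| 2 | 0.066 | 0.071 |
| 3 | 0.099 | 0.123 |
| 5 | 0.201 | 0.294 |

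Here 232 is 258 × 0.9. If the changed settings are more sensitive, e is negative. With true success at 55% and n = 122, P(pass) falls from 0.916 to 0.825 at −2 points and 0.607 at −5 points.

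**Step 7: margin in subjects.** At the expected rate, 0.55 × 122 = 67.1 successes against the 60 needed, a margin of about 7. For n = 232, 0.55 × 232 = 127.6 against 109, a margin of about 18. The planned analysis is Kaplan-Meier with log-log limits, so these binomial counts are approximate.

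**The case against.** The case for leaving the text alone has real force.

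- **The settings are not unobserved.** Sites confirm the parameters at every visit from Day 30, and 7.6 requires a printed programming report at insertion or for a pre-existing device. A reader might infer that changes go unrecorded and cannot be corrected for. The text does not support that. It supports only that a change after a recurrence need not be entered or justified in the EDC. Appendix A also leaves adjudication detail to the Phase 2 SAP.
- **The group is narrow.** An asymptomatic, automatically detected blanking episode does not meet the definition, and the Day 30 visit is nominally remote with no scheduled ECG.
- **Much of the PEE is immune.** ECG, patient-triggered, re-ablation, cardioversion and drug failures do not depend on AF or AT auto-detection. The simulated windows are also sparse: 270 / 30 = 9 intervals with two 2-minute windows each give 36 minutes, and two Holter days bring the total to about 48.6 of 270 × 24 = 6,480 hours.
- **Burden endpoints are descriptive.** Reprogramming after a post-blanking failure cannot change that subject's PEE result.

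All four points stand as limits on size. They do not close the gap. The permission still reaches subjects at risk for the PEE, and any overlap of a stored episode with a window counts, so long episodes can be caught by sparse windows. A descriptive summary meant to help set a standard also needs known settings.

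**Conclusion.** The point holds as a wording and documentation gap that is worth closing. As written, detection of stored AF and AT episodes after Day 90 can differ according to whether a subject had a qualifying recurrence during blanking, and the study database need not show that it did.

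The size and direction of any effect on the PEE cannot be determined from the documents. They give neither the share of subjects with a qualifying blanking recurrence, nor the share reprogrammed, nor the changes made. The figures in Steps 6 and 7 show only how far the test would move under assumed shifts; they do not estimate a shift.

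Two stronger readings should be avoided. One is that the PEE is biased towards success: more sensitive settings would push it the other way. The other is that nearly all the burden comes from PEE failures followed on freely chosen settings. Failures include acute procedural failure, drug use, cardioversion and re-ablation, and because the PEE simulates intermittent monitoring, PEE successes may carry burden too.

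**What to change.** - **Trigger.** In Appendix A 7.6, 7.10–7.13 and 7.15, make the trigger the first confirmed recurrence after the Blanking Period. Confirm that the Table 7.6-1 detection settings are in place when the evaluation period starts. The existing Day 90 parameter check can serve if its date is recorded, since that visit may fall anywhere from Day 76 to Day 104.
- **Record.** Enter every change of a detection parameter in the EDC with date, value and reason, whether before or after a recurrence.
- **Report and analyse.** State how many subjects had off-nominal settings after Day 90. Add a PEE sensitivity analysis that counts as failures those otherwise successful subjects who had off-nominal settings. This guards against a false pass from missed failures. Show the burden and longest-episode summaries with and without these subjects.

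The analysis should not be restricted to time at nominal settings. That would remove follow-up because of a recurrence and so censor informatively. There is also no need to hold settings fixed through Day 360: once a subject has failed the PEE after blanking, reprogramming cannot alter that result, and the log makes its effect on burden visible.

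The cost is slightly less freedom to reprogram during blanking, wording changes in six sections, one EDC field and one table. No sample-size figure changes.
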